4.3.2.2 Cytarabine

Cytarabine will be administered in the first cycle of induction at a dose of 200 mg/m² QD by IV for 7 days, immediately after the corresponding dose of idasanutlin. Dose and regimen can be lowered per investigator choice in the second induction cycle

Cytarabine will be administered in consolidation at a dose of 1.5 g/m² QD for 5 days as IV infusion over a minimum of 3 hours, immediately after corresponding dose of idasanutlin.

The dose of cytarabine should be calculated based on a body weight measurement within 2 days of the first day of each cycle. To calculate body surface area (BSA) for the cytarabine dose, refer to [Appendix 9](#).

4.3.2.3 Daunorubicin

Daunorubicin will be administered in induction at a dose of 60 mg/m² QD for 3 days as IV infusion, immediately after the corresponding dose of idasanutlin. Dose and regimen can be lowered per investigator choice in the second induction cycle.

The dose of daunorubicin should be calculated based on a body weight measurement within 2 days of the first day of each cycle. To calculate BSA for the daunorubicin dose, refer to [Appendix 9](#).

4.3.2.4 Premedication

Patient must receive premedication as outlined in [Table 6](#). Further details are provided in [Appendix 5](#).

Table 6 Premedication

| Timepoints | Premedication | Administration |
|---|--|--|
| Induction and consolidation All cycles | Anti-emetic medicines (second-generation anti-emetic medicines, such as palonosetron, ondansetron, or granisetron) | Mandatory prior to each idasanutlin dosing Dosing as per individual drug prescribing information |
| | Anti-diarrheal medicines (unless medically contraindicated) ^a | Mandatory prior to each idasanutlin dosing. Dosing as per individual drug prescribing information |
| | Anti-fungal agents | Strongly recommended prior Day 1 of Cycle 1 Dosing as per individual drug prescribing information (until neutrophil count recovery Grade ≤ 2) |
| | Antimicrobial medicines | Strongly recommended prior Day 1 of Cycle 1 Dosing as per individual drug prescribing information (until neutrophil count recovery Grade ≤ 2) |
| Maintenance All cycles | Prophylaxis may be utilized on the basis of investigator discretion and patient tolerability. Supportive therapies, including prophylaxis for diarrhea and nausea, are encouraged in the maintenance phase of the study | |

^a Contraindication should be recorded in the medical history or as a separate adverse event.

4.3.3 Investigational Medicinal Product Accountability

Idasanutlin, cytarabine, and daunorubicin are considered IMPs in this trial. Idasanutlin that is required for completion of this study will be provided by the Sponsor. Cytarabine and daunorubicin will be obtained from local sources.

The study site will acknowledge receipt of idasanutlin, using the IxRS to confirm the shipment condition and content. Any damaged shipments will be replaced.

IMPs will either be disposed of at the study site according to the study site's institutional standard operating procedure or be returned to the Sponsor (if supplied by the Sponsor) with the appropriate documentation. The IMP should only be returned to the Sponsor if

the site is unable to destroy IMP per their standard operating procedure. The site's method of destroying Sponsor-supplied IMPs must be agreed to by the Sponsor. The site must obtain written authorization from the Sponsor before any Sponsor-supplied IMP is destroyed, and IMP destruction must be documented on the appropriate form.

Accurate records of all IMPs received at, dispensed from, returned to, and disposed of by the study site should be recorded on the Drug Inventory Log.

4.3.4 Continued Access to Idasanutlin

Currently, the Sponsor does not have any plans to provide the Roche IMP idasanutlin or any other study treatments or interventions to patients who have completed the study. The Sponsor may evaluate whether to continue providing idasanutlin in accordance with the Roche Global Policy on Continued Access to Investigational Medicinal Product, available at the following web site:

http://www.roche.com/policy_continued_access_to_investigational_medicines.pdf

4.4 CONCOMITANT THERAPY

Concomitant therapy includes any medication (e.g., prescription drugs, over-the-counter drugs, herbal or homeopathic remedies, and nutritional supplements) or blood product (e.g., RBCs and platelets) used by a patient from 28 days prior to screening up to the study drug completion/discontinuation visit. All such therapies should be reported to the investigator and recorded on the Concomitant Medications eCRF. The investigator should instruct the patient to notify the investigator (or designee) about any new medications (including over-the-counter drugs and herbal/alternative medications) he/she takes after the start of study medication. Patients must be instructed not to take any additional medications (including over-the-counter products and herbal/alternative medications) during the study without prior consultation with the investigator (or designee).

4.4.1 Permitted Therapy

Patients are permitted to use the following therapies during the study:

- Oral contraceptives
- Hormone-replacement therapy

4.4.2 Prohibited Therapy

Use of the following therapies (excluding protocol-specified treatments) is prohibited during the study:

- Any anti-cancer therapy, approved or investigational, other than intrathecal CNS prophylaxis (except during HSCT consolidation)
- Hormonal therapy other than contraceptives, stable hormone-replacement therapy, or megestrol acetate
- Biologic agents other than hematopoietic growth factors

MDM2 antagonists were shown in vitro to affect all types of hematopoietic progenitors, including megakaryocytic differentiation. They inhibit both early and late stages of megakaryopoiesis, including ploidy and proplatelet formation (Mahfoudhi et al. 2016). As a consequence, the effect on early progenitors might induce long-lasting thrombocytopenia in vivo.

Therefore, because of the potential severity and duration of thrombocytopenia induced by study treatment, patients in clinical need of chronic treatment with oral or parenteral anticoagulant/antiplatelet agents (e.g., warfarin, chronic daily treatment with aspirin [> 325 mg/day], clopidogrel, dabigatran, apixaban, rivaroxaban, and systemic low-molecular weight heparin), or subcutaneous anticoagulant prophylaxis) are excluded from this study. For patients considered eligible for the study because they are able to tolerate interruption of anticoagulant or antiplatelet treatment, these agents must be discontinued 7 days (or 5 half-lives, whichever is shorter) prior to initiating study treatment (except used as flushes for indwelling catheters). After the study treatment completion or discontinuation visit, treatment with anticoagulant/antiplatelet agents may be re-initiated for patients with transfusion-independent adequate platelet levels as clinically indicated. An exception can be made for patients with stable blood parameters in need of prophylaxis or after consultation with the Medical Monitor if use is clinically needed. The maintenance of anti-thrombotic treatment should be continuously reassessed. Sustained use over time must be clinically warranted.

Oral or parenteral use of the following drugs will be prohibited during the treatment phase in order to prevent undesirable drug–drug interactions (DDIs).

- Strong/moderate inducers or inhibitors of CYP2C8, including gemfibrozil, which is also an inhibitor of UGT1A3 (see [Appendix 17](#), Table 1)
- CYP2C8 (see substrates or OATP1B1/3 substrates (see [Appendix 17](#), Table 3)
- Strong inducers of CYP3A4 (see [Appendix 17](#), Table 2)

Substrates and inhibitors ([Appendix 17](#), Table 1 and Table 3) must be discontinued 7 days prior to start of study treatment.

Inducers ([Appendix 17](#), Table 1 and Table 2) must be discontinued 14 days prior to start of study treatment.

Drugs listed in [Appendix 17](#) (Table 1, Table 2, and Table 3) may be re-initiated per protocol after the study drug completion or discontinuation visit.

Exception might be made upon discussion with the Medical Monitor based on the medical needs (such as anti-rejection drugs) and patient benefit. In such cases, decision will be clarified in a note to file and filed accordingly.

The above medications are not necessarily comprehensive. Thus, the investigator should consult the prescribing information for any concomitant medication as well as the

Internet references provided below when determining whether a certain medication should be inhibited by the above rationale. In addition, the investigator should contact the Medical Monitor if questions arise regarding medications not listed above.

- <http://www.fda.gov/downloads/Drugs/GuidanceComplianceRegulatoryInformation/Guidances/UCM292362.pdf>
- <http://medicine.iupui.edu/clinpharm/ddis/table.aspx>

4.5 STUDY ASSESSMENTS

The schedule of activities performed during the study is detailed in [Appendix 1](#).

4.5.1 Informed Consent Forms and Screening Log

Written informed consent for participation in the study must be obtained before performing any study-specific screening tests or evaluations. Informed Consent Forms for enrolled patients and for patients who are not subsequently enrolled will be maintained at the study site.

All screening evaluations must be completed and reviewed to confirm that patients meet all eligibility criteria before enrollment. The investigator will maintain a screening log to record details of all patients screened and to confirm eligibility or record reasons for screening failure, as applicable. Those patients who fail screening because of long waiting times for results or study technical reasons (such as, "cohort on hold") can be rescreened once at a later date if deemed eligible before the screen failure. The decision to rescreen individual patients will be made jointly by the Medical Monitor and the investigator and any other person the investigator or Medical Monitor considers necessary to assist with this decision. Any such decision and the reasons for it will be clearly documented. Any out-of-window assessments need to be repeated and undergo a complete review by the Medical Monitor. Patients deemed ineligible based on screening results for the following exclusion criterion will be allowed to be re-screened once:

- Infection considered by the investigator to be clinically uncontrolled or of unacceptable risk to the patient upon the induction of neutropenia, that is, patients who are or should be on antimicrobial agents for the treatment of active infection

Screening and pretreatment assessments will be performed within 14 days prior to Cycle 1, Day 1 unless otherwise specified. However, results of screening tests or examinations performed as standard of care prior to obtaining informed consent and within the protocol-defined window (prior to randomization/Cycle 1, Day 1) may be used rather than repeating required tests. If a bone marrow aspirate cannot be obtained or is not evaluable, a bone marrow biopsy must be performed for AML diagnostic purposes. If biopsy is performed at screening, a bone marrow sample should be provided for biomarker analysis.

Cytogenetic and molecular risk according to ELN standardized reporting system (see [Appendix 7](#) and [Appendix 8](#)) must be available from initial diagnosis prior to enrolment of the patient to allow risk category identification. At a minimum cytogenetic information allowing stratification into the two risk categories (favorable/intermediate versus adverse) needs to be available. Additional information on molecular markers is desirable and should be entered into the eCRF.

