3.1.3 Post-Consolidation Phase and Expansion Phase

The post-consolidation cohort of 30 patients is designed to further assess the safety and efficacy of idasanutlin given as a single agent to idasanutlin treatment-naïve patients in a maintenance setting. Patients will start maintenance right after consolidation completion.

The expansion phase is designed to further assess the safety and efficacy of idasanutlin in combination with cytarabine and daunorubicin at its RP2D in induction and in combination with cytarabine in consolidation followed by a single-agent maintenance.

The expansion phase (approximately 40 patients) is composed of two cohorts: 20 patients with favorable or intermediate risk and 20 patients with high risk (see [Table 3](#)).

All expansion patients will be enrolled and treated as described in [Table 4](#), and patients in the post-consolidation cohort will receive maintenance treatment as described in [Table 5](#).

In the expansion cohorts, patients who achieve remission after up to 2 induction cycles will receive chemotherapy consolidation treatment up to 4 cycles with 1.5 mg/m² cytarabine or allo-HSCT (as per site guidelines). Patients who achieved a confirmed remission at the end of chemotherapy consolidation or allo-HSCT or who underwent allo-HSCT in MLFS after induction will receive maintenance treatment for 12 cycles (see [Table 4](#)).

Patients receiving chemotherapy consolidation in the expansion should start maintenance right after consolidation completion. Patients receiving allo-HSCT consolidation should start within 90 days of the transplant and a full pre-transplant hematologic response assessment must be provided if the transplant is performed more than 4 weeks after end of induction.

On the basis of safety, tolerability, and clinical benefit and after consultation with the Medical Monitor, patients may be allowed to continue maintenance past 12 cycles.

Table 3 Post-Consolidation and Expansion Cohorts

| Cohorts | Population |
|---|---|
| Post-consolidation | Idasanutlin treatment-naïve patients in remission who received chemotherapy consolidation but were MRD positive after induction as locally assessed |
| Expansion: favorable or intermediate risk | Favorable and intermediate risk patients (ELN 2017; see Appendix 8) |
| Expansion: high risk | Adverse-risk patients (ELN 2017; see Appendix 8) and secondary AML defined as AML evolving from AHD |

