3.3.4.1 AML-Associated Mutations, *MDM2* Protein Expression, *MIC-1* Secretion and Gene Expression

The mutation status of *TP53* as well as mutations of other genes with clinical relevance or prognostic value including *FLT-3*, *IDH1* and *IDH2* will be assessed by a sequencing panel. *MDM2* expression in AML cells in pretreatment blood specimens in patients with AML will be assessed by multi-color flow cytometry. *Mic-1* secretion will be analyzed by ELISA. Various gene expression signatures have been explored for their predictive value for *MDM2* inhibitors. In this study, gene expression profiling is planned to clinically validate and explore additional signatures.

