4.1.2.2 Exclusion Criteria for Patients in the Phase Ib Dose-Escalation Phase Only

Patients who meet the following exclusion criterion will be excluded from enrollment in the dose-escalation cohort in any part of the study:

- Adverse risk patients as per ELN 2017 criteria (see [Appendix 8](#))

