Appendix 8 European LeukemiaNet Standardization Reporting System

2017 ELN Risk Stratification by Genetics

| Risk category* | Genetic abnormality |
|----------------|--|
| Favorable | t(8;21)(q22;q22.1); RUNX1-RUNX1T1 |
| | inv(16)(p13.1q22) or t(16;16)(p13.1;q22); CBFB-MYH11 |
| | Mutated NPM1 without FLT3 -ITD or with FLT3 -ITD ^{low†} |
| | Biallelic mutated CEBPA |
| Intermediate | Mutated NPM1 and FLT3 -ITD ^{high†} |
| | Wild-type NPM1 without FLT3 -ITD or with FLT3 -ITD ^{low†} (without adverse-risk genetic lesions) |
| | t(9;11)(p21.3;q23.3); MLLT3-KMT2A * |
| | Cytogenetic abnormalities not classified as favorable or adverse |
| Adverse | t(6;9)(p23;q34.1); DEK-NUP214 |
| | t(v;11q23.3); KMT2A rearranged |
| | t(9;22)(q34.1;q11.2); BCR-ABL1 |
| | inv(3)(q21.3q26.2) or t(3;3)(q21.3;q26.2); GATA2,MECOM(EVI1) |
| | -5 or del(5q); -7; -17/abn(17p) |
| | Complex karyotype, [§] monosomal karyotype |
| | Wild-type NPM1 and FLT3 -ITD ^{high†} |
| | Mutated RUNX1 [†] |
| | Mutated ASXL1 [†] |
| | Mutated TP53 [*] |

Notes: Frequencies, response rates, and outcome measures should be reported by risk category, and, if sufficient numbers are available, by specific genetic lesions indicated.

* Prognostic impact of a marker is treatment-dependent and may change with new therapies.

† Low, low allelic ratio (<0.5); high, high allelic ratio (≥0.5); semiquantitative assessment of *FLT3*-ITD allelic ratio (using DNA fragment analysis) is determined as ratio of the area under the curve “*FLT3*-ITD” divided by area under the curve “*FLT3*-wild type”; recent studies indicate

Appendix8: European LeukemiaNet Standardization Reporting System (CONT.)

that AML with *NPM1* mutation and *FLT3*-ITD low allelic ratio may also have a more favorable prognosis and patients should not routinely be assigned to allogeneic HCT.

‡ The presence of t(9;11)(p21.3;q23.3) takes precedence over rare, concurrent adverse-risk gene mutations.

§ Three or more unrelated chromosome abnormalities in the absence of 1 of the WHO-designated recurring translocations or inversions, that is, t(8;21), inv(16) or t(16;16), t(9;11), t(v;11)(v;q23.3), t(6;9), inv(3) or t(3;3); AML with *BCR-ABL1*.

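### Section 4.5.1 accepts cytogenetics alone for risk assignment, which cannot deliver the ELN 2017 split that defines the cohorts, so adverse-risk patients could be counted in the favorable/intermediate CR estimate

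*Combined protocol and SAP*

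**What the plan says.** Section 4.5.1 opens its paragraph on risk by saying that cytogenetic and molecular risk under the ELN system "must be available from initial diagnosis prior to enrolment of the patient to allow risk category identification". The next sentence reads "At a minimum cytogenetic information allowing stratification into the two risk categories (favorable/intermediate versus adverse) needs to be available", and the one after it "Additional information on molecular markers is desirable and should be entered into the eCRF".

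The cohorts rest on the full ELN 2017 scheme. Table 3 in Section 3.1.3 defines the favorable/intermediate expansion cohort by ELN 2017 with reference to Appendix 8. It defines the high-risk cohort as ELN 2017 adverse risk "and secondary AML defined as AML evolving from AHD". Section 4.1.2.2 excludes from dose escalation "Adverse risk patients as per ELN 2017 criteria".

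The table in Appendix 8, headed "2017 ELN Risk Stratification by Genetics", places in the adverse group wild-type NPM1 with a high FLT3-ITD ratio, and mutated RUNX1, ASXL1 and TP53.

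Section 6.3 analyses the cohorts separately and pools dose-escalation patients treated at the RP2D into the favorable/intermediate cohort. Section 6.1 counts those patients within the 20.

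**The concern.** The first sentence in Section 4.5.1 demands molecular risk; the next two let a site enrol without it. A site can meet the stated minimum and still lack what is needed to separate ELN 2017 favorable/intermediate from adverse. Such patients could enter by two routes, dose escalation and the expansion cohort, and pooling at the RP2D brings both into one estimate.

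CR at the end of induction is the primary efficacy endpoint, and Section 6.1 gives each risk group its own reference: 65%–80% expected under 7+3 for favorable/intermediate (with 65% to be ruled out), and up to 50%–55% for high risk. Adverse-risk patients counted in the first group could lower its estimate, and the high-risk cohort would lack the same patients.

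**Working it through.** **Is there a later correction?** Four places could supply one.

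- Section 4.2 requires eligibility documents and Sponsor approval, but does not name molecular data.
- Appendix 1 (Tables 1 and 4) lists determination of cytogenetic and molecular risk at screening, without saying what happens if the molecular part is missing.
- Section 6.3 analyses by cohort and contains no reclassification.
- Section 6.3.3 repeats the endpoints in patients with wild-type p53. That addresses TP53 but leaves RUNX1, ASXL1 and NPM1/FLT3-ITD.

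None reassigns patients or plans CR by final ELN category.

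**Reproducing the plan's figure.** Table 15 uses two-sided 90% Clopper-Pearson intervals with N = 20. The lower limit for x remissions is the 5% quantile of Beta(x, 21 − x); the upper limit is the 95% quantile of Beta(x + 1, 20 − x).

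- 17/20: 65.6% to 95.8%, printed as (66, 96). It reproduces.
- 16/20: 59.9% to 92.9%, printed as (60, 93). It reproduces.

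So 17 is the smallest count whose lower limit exceeds 65%.

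**Illustrating dilution.** Inputs:

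- N = 20 and the 17/20 reference (Section 6.1, Table 15).
- True favorable/intermediate CR of 85%: an assumption, equal to the highlighted row of Table 15.
- Adverse-risk CR q of 50%, 55% or 70%: an assumption. The first two are the 7+3 figures for high risk in Section 6.1; 70% is the observed high-risk level that the section discusses.
- Number misassigned, k: not in the documents; 0, 2 and 4 are shown.

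Expected CR = [(20 − k) × 0.85 + k × q] / 20. The chance of at least 17 remissions is the sum over j = 0 to k of P(Bin(k, q) = j) × P(Bin(20 − k, 0.85) ≥ 17 − j).

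| k of 20 | q | Expected CR | P(≥17/20) |
|---|---|---|---|
| 0 | – | 85.0% | 64.8% |
| 2 | 50% | 81.5% | 47.6% |
| 2 | 55% | 82.0% | 50.1% |
| 2 | 70% | 83.5% | 57.5% |
| 4 | 50% | 78.0% | 31.5% |
| 4 | 55% | 79.0% | 36.0% |
| 4 | 70% | 82.0% | 50.1% |

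To more places, the 57.5% and 31.5% entries are 57.45% and 31.47%, hence 57% and 31% as whole numbers. Each misassigned patient lowers expected CR by (85 − q)/20 points: 1.75 at q = 50%, 1.5 at 55%, 0.75 at 70%.

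**Direction of error.** If the true favorable/intermediate CR is only 65%, the chance of at least 17/20 is 4.4% with k = 0. With k = 4 and q of 50%–55% it is 2.4%–3.0%. Dilution by patients with CR no higher than 65% does not create false positives.

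**The case against.** The strongest reply is that a possibility is being priced as if it were a fact. A reader might infer that adverse-risk patients will be in this cohort. The documents do not show that: the same paragraph asks for molecular risk, the schedule lists it at screening, and the Sponsor reviews each patient. Appendix 8 narrows the gap further. Its footnotes associate TP53 mutation with complex and monosomal karyotype, so cytogenetics would catch some cases, and they discount certain markers that occur with favorable-risk subtypes. Secondary AML is excluded separately by history (Section 4.1.2.4). All of this stands, and it limits the point to what could happen. It does not close the gap for patients without molecular results.

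A reader might also infer that the comparison with 65% is invalid. That is not established. Section 6.1 does not say how the patients behind the 65%–80% figure were risk-classified, and its cited sources date from 2009 to 2016, before the ELN 2017 publication. If they were classified by cytogenetics, the benchmark contains a similar mix and the bias against it is smaller.

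The illustration is also sensitive to its inputs. The 50%–55% is for 7+3 alone and for high-risk patients as a whole, including secondary AML. Using it beside 85% credits benefit from the combination only to favorable/intermediate patients, which is why 70% is shown too. Further, 17/20 illustrates precision; it is not a decision rule. The primary analysis is estimation, and Section 6.8 calls the study hypothesis-generating.

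Finally, Appendix 8 carries a note that response rates should be reported by risk category. Section 6 does not turn that note into an analysis.

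**Conclusion.** The point holds as a contradiction within Section 4.5.1, and as a mismatch between its minimum and the ELN 2017 definitions in Sections 3.1.3 and 4.1.2.2. Following the minimum could put ELN-adverse patients into the favorable/intermediate CR estimate and lower it.

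The size is unknown. Under the stated assumptions, two misassigned patients of 20 cost 7 to 17 percentage points of the chance of reaching 17/20 (64.8% − 57.5% and 64.8% − 47.6%), and four cost 15 to 33 points (64.8% − 50.1% and 64.8% − 31.5%). These figures show sensitivity; they do not forecast the bias. The issue merits correction before analysis but does not undermine the trial.

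**What to change.** 1. Reconcile the three sentences in Section 4.5.1 with each other and with Sections 3.1.3 and 4.1.2.2. Removing the cytogenetics-only allowance just where local molecular results exist would not help, because the gap concerns patients without results.
2. Pre-specify CR by final ELN 2017 category, derived from cytogenetics plus baseline molecular data (local results in the eCRF and screening sequencing). Report it alongside CR by cohort as enrolled, and show patients lacking molecular data separately. Because reclassification happens at analysis, treatment need not wait for sequencing.
3. Confirm that the panel can support an ELN class. Section 3.3.4.1 plans sequencing of TP53 "as well as mutations of other genes with clinical relevance or prognostic value including" FLT3, IDH1 and IDH2; it does not name NPM1, RUNX1 or ASXL1. Appendix 8 determines the FLT3-ITD allelic ratio by DNA fragment analysis, so that source needs stating. Section 4.5.8.3 allows that some collected samples may not be analysed; the samples needed here should be protected from that.
4. State how the patients behind the 65%–80% benchmark were risk-classified.

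The cost is a wording change, a pre-specified table and use of baseline samples already planned, plus added testing if the panel proves incomplete. Category sizes may differ from 20, and some patients may remain unclassifiable.
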